Title:

Young adults' responses to e-cigarette advertisement features and the effect of restricting features on tobacco use (K99DA046563)

NCT: NCT04249219

Date: 7/26/2023

Study Protocol:

RESEARCH DESIGN

K99 Phase: Aim 1:

The purpose of the K99 Phase is to identify which e-cigarette ad features most strongly influence young adults' attitudes, susceptibility, and intentions to use e-cigarette.

Participant Recruitment and Screening. We will recruit 65 young adults susceptible to e-cigarette use to complete the study. Participants will be recruited from the greater Worcester, Massachusetts area using email, flyers, and social media, advertising an opportunity to participate in a health messaging study. Inclusion criteria are as follows: 1) 18-26 years old and 2) reporting never trying an e-cigarette, not even a puff. Susceptibility to EC use, will be determined using the Susceptibility to Use Tobacco Products questionnaire.¹³ Only those who select "very unlikely" for all three susceptibility questions, will be excluded from the study. All others will be considered susceptible to use.

Procedures. Following confirmation of eligibility and informed consent, participants will complete sociodemographic questions and a pre-exposure questionnaire. Then participants will view an e-cigarette print advertisement that includes one or more of the following popular feature categories:⁷ 1) brand, 2) descriptor, 3) modeling, and 4) warning. A monitor on the computer will track the participant's eye movements and two sensors on the participant's fingers will track heart rate and skin conductance. Each advertisement will appear for ten seconds. After each advertisement, participants will answer a post-exposure questionnaire with items pertaining to perceptions about e-cigarettes. This process will be repeated 14 additional times, resulting in a total of 15 different advertisements seen by participants. All methods are consistent with accepted standards of psychophysiological measurement for media studies.

Measures. Psychophysiological measures will include: 1) Visual attention assessed using eye-tracking, It will determine dwell time on areas of interest (brand, descriptor, modeling, warning) and collect data dwell time, 2) Attention, conceptualized as cognitive resources allocated to encode a message into working memory will be operationalized as heart rate, 3) Arousal, an indicator of physiological activation in the sympathetic nervous system, will be measured by sampling skin conductance. Self-report measures will be collected through iMotions, a secure web application for building and managing surveys and collection of psychophysiological data.

Data Analytic Plan: Self-report scores motivation to avoid e-cigarettes were averaged for each participant, and then averaged across participants to create a mean score for each advertisement and brand. Psychophysiological scores for each construct (i.e., heart rate, skin conductance, visual attention) were also averaged across participants to create a mean score for each advertisement. The lowest scores for the self-report and heart rate data were ranked highest. For visual attention and skin conductance, highest scores were ranked highest. Using a multi-attribute decision-making model, we created a decision matrix in which each row (e.g., alternative or message) represented an advertisement and each column (attribute) represented a construct collected via the self-report or psychophysiological data. The rank of each attribute was summed within each message to create a total rank for each message by study type (self-report, psychophysiological).

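### Ads are ranked on simple across-participant means with no participant term; if single trials are lost, between-person level adds noise to the ranks that a random-intercept model would largely remove

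*Combined protocol and SAP*

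**What the plan says.** The design is within-person. Participant Recruitment and Screening sets the sample: "We will recruit 65 young adults susceptible to e-cigarette use to complete the study". Under Procedures, exposures repeat, "resulting in a total of 15 different advertisements seen by participants". "Each advertisement will appear for ten seconds", eye movements are tracked, and "two sensors on the participant's fingers will track heart rate and skin conductance". A questionnaire follows every ad.

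The Data Analytic Plan reduces these repeated measurements to one number per ad and construct. Self-report scores "were averaged for each participant, and then averaged across participants to create a mean score for each advertisement and brand". For the sensor data, "Psychophysiological scores for each construct (i.e., heart rate, skin conductance, visual attention) were also averaged across participants". The ad means are ranked within each construct, and then "The rank of each attribute was summed within each message to create a total rank for each message by study type".

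No participant effect, within-person centring, baseline correction or rule for lost trials is described. The text does not say whether heart rate and skin conductance are levels or changes, whether everyone saw the same 15 ads, or in what order. The pre-exposure questionnaire in Procedures is not used to adjust the scores. The one general assurance, "All methods are consistent with accepted standards of psychophysiological measurement for media studies", concerns measurement and settles none of these points.

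**The concern.** People differ in resting heart rate, skin conductance and habitual looking time. A simple mean over participants is a fair basis for comparing ads only when each ad's mean covers the same people, so that personal level cancels in every comparison. Once some participants contribute to one ad but not to another, part of the difference between the two means reflects who was measured and not what the ad did.

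An eye tracker and finger sensors recording over ten-second exposures can plausibly lose single trials, although the documents give no rate. The ad ranking is the output of this analysis, so noise in the ad means passes directly into it. If loss is random this costs precision and does not cause bias.

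**Working it through.** The plan gives no precision, power or error figure to reproduce. The check compares simple ad means with participant-adjusted ad means.

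**Inputs from the documents:** n = 65 participants; 15 ads each; simple means across participants; ranks summed over constructs.

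**Assumed inputs (not in the documents):** share of trials lost m = 0, 2, 5, 10 or 20%, at random; ratio r of between-person to within-person SD, from 0 to 6; SD of the true ad effects, 0.2 or 0.4 within-person SDs. Ratios of 0.33 to 1 stand for scores with little personal level, such as changes from baseline. Ratios of 2 to 6 stand for raw levels.

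**Formula.** Let the score be ad effect + person level (variance τ²) + error (variance σ²), with f = 1 − m the share of trials kept.

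- Each ad mean has variance (τ² + σ²)/(nf).
- Two ad means share people, so their covariance is τ²/n.
- A difference of simple means therefore has variance 2(σ² + mτ²)/(nf).
- Adjusting for participant brings this close to 2σ²/(nf).
- Inflation is about 1 + r²m, with r = τ/σ.

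Example with m = 0.10, r = 2, σ = 1: nf = 65 × 0.9 = 58.5. Simple means give 2(1 + 0.1 × 4)/58.5 = 0.048; adjusted means give 2/58.5 = 0.034; the ratio is 1.40.

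**Inflation from the formula**

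| Trials lost | r = 0.33 | r = 1 | r = 2 | r = 6 |
|---|---|---|---|---|
| 2% | 1.00 | 1.02 | 1.08 | 1.72 |
| 5% | 1.01 | 1.05 | 1.20 | 2.80 |
| 10% | 1.01 | 1.10 | 1.40 | 4.60 |
| 20% | 1.02 | 1.20 | 1.80 | 8.20 |

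**Simulation, one construct** (1,500 studies per setting, variance ratio estimated from each data set; 10% loss, ad SD 0.2)

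| r | Inflation | Rank correlation with true order, simple | Adjusted |
|---|---|---|---|
| 0.33 | 1.01 | 0.795 | 0.795 |
| 1 | 1.09 | 0.775 | 0.787 |
| 2 | 1.40 | 0.744 | 0.793 |
| 6 | 4.63 | 0.529 | 0.786 |

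With ad SD 0.4 the correlations are 0.91–0.92 simple against 0.92 adjusted for r of 0.33 to 1, and 0.77–0.90 against 0.92 for r of 2 to 6.

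**Simulation, summed psychophysiological rank** (900 studies per setting, loss independent by construct, 10% loss)

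| r for heart rate / skin conductance / visual attention | Simple v adjusted, ad SD 0.2 | Simple v adjusted, ad SD 0.4 |
|---|---|---|
| 0.33 / 0.33 / 0.33 | 0.74 v 0.75 | 0.89 v 0.89 |
| 2 / 1 / 0.5 | 0.72 v 0.75 | 0.88 v 0.89 |
| 6 / 4 / 1 | 0.61 v 0.75 | 0.81 v 0.89 |

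At 2% loss the 6/4/1 scenario gives 0.73 v 0.77 and 0.88 v 0.90.

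**Cases with no effect.** Complete data, and 10% loss of whole participants, give identical ranks.

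**Cost of adjusting.** Over all settings the adjusted correlation was at worst 0.002 below the simple one, which is within simulation error. A REML random-intercept fit gave the same rank list as the adjusted means used here in 97 of 100 data sets.

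**Second simulation**, by intraclass correlation (ICC), where r² = ICC/(1 − ICC), with ad SD 0.25. At 10% loss, inflation was 1.04, 1.09, 1.22 and 1.91 for ICC 0.3, 0.5, 0.7 and 0.9, in line with the formula. At ICC 0.9 (r = 3) the truly top ad was ranked first in 49% of studies with simple means and 58% with adjusted means. Some REML fits in this set gave convergence warnings, so its figures come from generalised least squares.

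**Position term.** With complete data, order random per person and ad SD 0.2, adding position changed the correlation from 0.80 to 0.80 for a decline of 0.5 SD over the session, and from 0.79 to 0.80 for 1.0 SD.

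**The case against.** The strongest reply is that nothing goes wrong under the design as written. Every participant sees 15 ads, no lost trials or differing ad sets are mentioned, and with complete data the adjustment changes nothing. That stands, and it is why the concern is conditional.

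Second, every decisive input is assumed, and the largest figures come from an extreme corner: r = 6 is an ICC of 36/37 = 0.97. At ICC 0.3 to 0.5 and 10% loss, the second simulation gave correlations of 0.837 v 0.841 and 0.831 v 0.841, which is no practical difference. This also stands. The r = 6 figures are arithmetically sound (two repeat simulations gave inflation of 4.51 and 4.69 at 10% loss), but they mark an upper end and are not an expectation.

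Third, summing ranks dilutes the effect, the plan states no cut-off or decision based on the ranks, and its stated purpose concerns ad features, not whole ads. The dilution is real and is shown above. The gain cannot be tied to a stated decision, but the ranking is what this analysis delivers.

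Fourth, nothing suggests that questionnaire answers given after each ad would be partly missing, and the position term gains almost nothing. Both are fair. The case rests mainly on the sensor data, and position is secondary.

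Finally, the plan is written in the past tense, so the analysis appears to have been done. That limits the remedy to re-analysis and reporting, both still possible. None of these points shows a setting in which simple means do materially better.

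**Conclusion.** The concern holds as a conditional one. The plan ranks ads on simple means of repeated measurements, and partial loss of trials would let between-person level into the ranks. How much cannot be known from the documents: it is negligible if few trials were lost or scores are changes with little personal level, and substantial only if raw levels were used and loss was appreciable. The conclusion assumes that trials are lost at random; loss that depended on both person and ad could bias the simple means. Because the better method is nearly free and never materially worse, the change should be made. This does not mean that the existing ranking is wrong.

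**What to change.** For each construct, fit a mixed model with ad as a fixed effect and a participant random intercept, adding presentation position (1–15) where order varied between people. Rank the adjusted ad means and sum the ranks as now; the decision matrix is unchanged.

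Report the ad order, whether each score is a level or a change, and the number of trials lost per ad and construct, so that a reader can judge whether the issue arises. If one fixed order was used, say that ad and position effects cannot be separated.

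The cost is a change of analysis wording and a standard model on data already collected. The downside is a little more analysis work, with no visible gain if the data prove nearly complete.

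### Aim 1 asks which ad features matter most, but the analysis ends in a rank per advertisement and no step links ad scores to features

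*Combined protocol and SAP*

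**What the plan says.** The combined protocol and SAP states the aim under Research Design, K99 Phase: Aim 1: "The purpose of the K99 Phase is to identify which e-cigarette ad features most strongly influence young adults" and, specifically, their attitudes, susceptibility and intentions. Under Procedures, participants "view an e-cigarette print advertisement that includes one or more of the following popular feature categories": "1) brand, 2) descriptor, 3) modeling, and 4) warning". Each participant sees 15 ads. Under Measures, eye-tracking records "dwell time on areas of interest (brand, descriptor, modeling, warning").

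The Data Analytic Plan then takes these steps:

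- Self-report scores are averaged to a mean per advertisement and per brand.
- Heart rate, skin conductance and visual attention "were also averaged across participants to create a mean score for each advertisement".
- The scores are ranked and placed in a decision matrix in which "each row (e.g., alternative or message) represented an advertisement and each column (attribute) represented a construct collected".
- "The rank of each attribute was summed within each message to create a total rank for each message by study type", with self-report and psychophysiological data kept apart.

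The plan ends there.

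**The concern.** The question is about features, but the answer the plan produces is about advertisements. An ad may carry several features, so its rank does not show which feature produced it. An ad with both a brand and a model in it could rank first because of either, both together, or something else in that ad.

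Followed as written, the plan gives a list of ranked ads and no estimate, with uncertainty, of any feature's influence. A statement that one feature matters more than another would be an informal reading of the ads near the top. The study title also concerns the effect of restricting features, so features are what the results will be used to judge.

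**Working it through.** **Step 1. What each analysis step produces.** The plan states no figure to reproduce here, so the first check sets the steps against the aim.

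| Step in the Data Analytic Plan | Unit of the output |
|---|---|
| Self-report means | advertisement, and brand |
| Heart rate and skin conductance means | advertisement |
| Visual attention mean | advertisement |
| Decision matrix | advertisement by construct |
| Summed rank | advertisement, by study type |

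No step codes ads by feature, compares ads with and without a feature, models scores on features, or compares dwell time between the four areas. The brand mean is not described as entering the matrix or as being set against another feature.

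The word feature is itself undefined. If it means presence of a category, 0 of 4 effects are given. If it means variants within a category (for example, which brand), at most 1 of 4 categories has a summary: brand, for self-report only, with no interval.

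**Step 2. How much data is reduced.** From the documents: 65 participants and 15 ads, so 65 × 15 = 975 participant-by-ad records. Each ad carries 1 to 4 categories. Taking one area of interest per feature present, there are 975 × 1 = 975 to 975 × 4 = 3,900 feature-area dwell times. The plan describes one visual-attention mean for each of the 15 ads.

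**Step 3. Could the same data answer the question?** That depends on which features each ad carries, which the documents do not give. The layouts below are assumptions. The design matrix X has an intercept and four 0/1 feature columns over 15 ads. An effect is estimable if X separates its column from the others.

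| Assumed layout | Rank of X (5 needed) | Effects estimable |
|---|---|---|
| A: each of the 2⁴ − 1 = 15 non-empty combinations once | 5 | 4 of 4 |
| B: brand on every ad; 8 combinations of the other three, 7 repeated | 4 | 3 of 4 (not brand) |
| C: descriptor and modeling always together; 7 non-empty combinations of brand, pair and warning, twice, plus one again | 4 | 2 of 4 (brand, warning) |
| D: brand and warning on every ad; descriptor and modeling always together, on 7 of 15 ads | 2 | 0 of 4 |
| E: brand on 14 of 15 ads (8 combinations of the other three, 6 repeated, plus one unbranded ad with descriptor and warning) | 5 | 4 of 4 |

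Even in layout A, 11 of the 15 ads carry more than one feature, so ad ranks would not separate the features without a model.

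**Step 4. Precision in layouts A and E.** Set the within-person SD to 1 and let τ be the SD between ads not explained by features (assumed, 0 to 0.3). With complete data from all 65 participants:

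SE_j = √( [(X′X)⁻¹]_jj × (1/65 + τ²) )

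95% half-width = t(0.975, 15 − 5 = 10 df) × SE_j = 2.228 × SE_j

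For layout A, [(X′X)⁻¹]_jj = 0.2727 for every feature. At τ = 0.3, SE = √(0.2727 × (0.0154 + 0.09)) = 0.170, and 2.228 × 0.170 = 0.38.

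| τ | A: SE, any feature | A: half-width | E: SE, brand | E: half-width, brand |
|---|---|---|---|---|
| 0 | 0.065 | 0.14 | 0.140 | 0.31 |
| 0.1 | 0.083 | 0.19 | 0.180 | 0.40 |
| 0.2 | 0.123 | 0.27 | 0.265 | 0.59 |
| 0.3 | 0.170 | 0.38 | 0.366 | 0.82 |

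In layout E the other three features have half-widths from about 0.15 to 0.40. If feature effects also vary between participants with an assumed SD of 0.3, 0.09/65 is added to the variance, and the layout A half-widths become 0.17, 0.20, 0.29 and 0.39.

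**The case against.** The best case for the plan has four parts.

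- **Dwell time.** Visual attention is defined by area, and the plan says only that scores were averaged over people. It never says the four areas were pooled, so area-specific means per ad remain possible. But the plan lists visual attention as one construct with one mean score per ad, and on either reading no comparison between areas is described.
- **The ad set may carry the answer.** Ads with a single feature are allowed, and if many ads isolate a feature the ranking is more informative than it looks. The brand mean also shows one summary above ad level. This cannot be judged without the layout. Even a favourable layout would still need a comparison of ads by feature, and none is planned.
- **The precision figures are hypothetical.** This is fair. The layouts, τ and the slope SD are assumptions, and they describe what an added model could achieve, not the harm in the present plan. The 10 df applies only to layouts A and E; the ad-level residual df is 15 − 4 = 11 in B and C and 15 − 2 = 13 in D. The finding itself rests on the text.
- **The remedy is not unique or complete.** A simpler ad-level contrast with an interval would also serve, and dwell time can reflect the size of an area. Separately, Aim 1 names attitudes, susceptibility and intentions, while the self-report score analysed is motivation to avoid e-cigarettes. A feature model alone does not resolve that mismatch.

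None of these supplies a step from ad scores to features.

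**Conclusion.** The concern holds and must be fixed. This is a mismatch between aim and analysis, not a missing detail: carried out exactly as written, the plan cannot say which feature matters most. It yields 0 of 4 feature effects or, on the within-category reading, an unadorned self-report summary for 1 of 4 categories. That conclusion needs no assumption beyond the text.

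How much can be recovered is uncertain. Under the assumed layouts it runs from all four effects to none. Where all four are estimable, half-widths run from 0.14 to 0.82 within-person SDs, depending on the layout and on τ.

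**What to change.** 1. Add a table of 15 rows showing which of the four categories each ad carries, and state whether feature means presence of a category or variants within it.
2. Add a feature-level analysis of the participant-by-ad data: for each outcome, a mixed model with feature indicators coded to that definition, and random effects for participant (with feature slopes if the data support them) and for advertisement. Report each estimable effect with a 95% confidence interval.
3. Summarise dwell time by feature area among the ads that carry the feature.
4. Keep the ad ranking as a descriptive result.
5. The Data Analytic Plan is written in the past tense. If the ranking was done before this analysis is added, label the addition post hoc.
6. If a feature is on every ad, or always paired with another, say that its separate effect cannot be estimated. If no feature effect can be estimated, restate the aim and conclusion as ranking advertisements.

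The cost is one table, analysis wording and programming, with no new data. The drawbacks are wide intervals with only 15 ads, precision that depends on a layout not yet stated, and probable post hoc status.
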